Appendix Table 3. Urinalysis Laboratory Abnormalities of Interest

Test	Markedly Abnormal Criteria
Protein in urine	> 1+
Blood in urine	Positive (+)
RBCs in urine	>0

Appendix Table 4. Vital Sign Abnormalities of Interest

Variable	Units	Markedly Abnormal Criteria Lower limit	Markedly Abnormal Criteria Upper limit
Systolic blood pressure	mmHg	<90	>140
Diastolic blood pressure	mmHg	<40	>90
Pulse rate	beats/minute	<60	>130
Respiratory rate	breaths/min	<12	>20
Temperature	°C	<36.0	>38.0
Weight	kg	Decrease of 7% or more	NA

NA = not applicable

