8. INVESTIGATIONAL PLAN

8.1. Overall Study Design

This is an open-label, multi-center study to evaluate the safety and tolerability of eteplirsen in patients 4 to 6 years of age with genotypically confirmed DMD with genetic mutations amenable to treatment by exon 51 skipping. In addition, this study will enroll an untreated control group (DMD patients not amenable to exon 51 skipping) to further evaluate the natural history of DMD in this patient population.

All patients will be evaluated for inclusion during a Screening/Baseline period. Written informed consent from the parent/legal guardian to participate in the study must be obtained prior to beginning any study-related procedures. Once eligibility is confirmed, all patients will undergo Screening Assessments as indicated in [Sections 2 and 3](#) (Schedule of Events).

For patients in the eteplirsen group, blood samples collected at the Screening Visit for the safety lab assessments must be obtained within 3 weeks prior to the Week 1 visit, and results must be available prior to dosing at Week 1.

- However, if more than 3 weeks have elapsed since the collection of blood samples for the Screening safety lab assessments, it must be repeated.
- If less than 3 weeks have elapsed since the collection of blood samples for the Screening safety lab assessments, additional safety lab assessments do not need to be performed, and the patient may proceed with Week 1 assessments as indicated in [Section 2](#).

Starting at Week 1, patients amenable to exon 51 skipping (treated patients) will receive once weekly IV infusions of 30 mg/kg eteplirsen for up to 96 weeks. An extension to the dosing period may be considered prior to the end of the 96-week planned dosing period.

Safety will be assessed through the collection of AEs, laboratory tests, electrocardiograms (ECGs), echocardiograms (ECHOs), vital signs, and physical examinations throughout the study.

Upon qualification for the study, patients enrolled into the eteplirsen group will undergo the baseline assessments including a muscle biopsy, which may occur at a different study site (denoted as the surgical unit) than where patients will undergo infusions and study assessments (denoted as the infusion site). Eteplirsen-treated patients will be randomized to a second muscle biopsy scheduled at Week 48 or Week 96. CCI

[REDACTED]

[REDACTED]

[REDACTED] CCI

[REDACTED]

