11.3.2. Vital Signs and Weight

For eteplirsen-treated patients, vital signs (blood pressure, heart rate, respiration, and temperature) and weight will be measured at the time points specified in [Section 2](#).

For infusion visits, vital signs are to be collected within approximately 30 minutes prior to infusion and approximately 5, 30, and 60 minutes after the end of the infusion. If the patient has not experienced an infusion reaction after the first year of treatment, vital signs may be reduced to pre-infusion and 30 minutes after the end of infusion. All assessments will be performed after patients have remained seated for 5 minutes.

Pulse rate and respiratory rate should be measured over 1 minute.

Details about how weight measurements are obtained are provided in the Clinical Evaluator Manual. If a patient's weight varies by more than 10% from the prior visit, the patient should be re-weighed to confirm the result, and an explanation of the change should be documented.

Patients in the untreated control group will have their vital signs and weight recorded at the time points specified in [Section 3](#).

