5.8.5 Vital Signs and Other Physical Findings

Vital signs, height/length, and weight will be summarized by treatment group and by selected time point. Baseline value, highest/lowest postbaseline value, and final observation and the corresponding change from Baseline will be summarized for treated patients, untreated patients. Highest/lowest value is considered as the largest absolute change from Baseline for systolic blood pressure, diastolic blood pressure, and respiratory rate, and highest value for pulse rate and temperature. The highest/lowest value will not be summarized for height, weight, or ulnar length. Frequency tables of patients with potentially clinically significant vital sign values will be generated. The

total number of potentially clinically significant values will also be summarized. Potentially clinically significant values can be found in Appendix 1 Table 4.

Vital signs will be listed for all patients. In addition, values meeting the predefined markedly abnormal criteria will be presented in a data listing. Treatment-emergent abnormalities will be indicated. Height and weight will also be listed.

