Appendix Table 5. Electrocardiogram and Echocardiogram Abnormalities of Interest

Variable	Units	LLN	ULN	Age Group (years)	Markedly Abnormal Criteria
Heart rate	Beats per minute	60	130		NA
QTcF interval	msec	NA	NA	All	Screening Visit >450
				<12	>480
				≥12	>500
				All	<320 Increase >60 >450 >480 >500
QRS interval	msec	NA	NA	<12	IVCD or any QRS conduction disturbance with a QRS >110 msec
				≥12	IVCD or any QRS conduction disturbance with a QRS >120msec
PR interval	msec	NA	NA	<12	>190
				≥12	>220
Left ventricular ejection fraction	%	NA	NA	All	<55%
Fractional shortening	%	NA	NA	All	<29%

IVCD = intraventricular conduction delay; LLN = lower limit of normal; NA = not applicable; QTcF= QT interval Fridericia corrected; ULN = upper limit of normal

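### Except for weight, the vital-sign abnormality limits carry no change-from-baseline condition, and the patient count built on them has no stated treatment-emergent rule or denominator of readings, so it may discriminate poorly

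*SAP*

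**What the plan says.** Incidence of vital-sign abnormalities is one of the listed safety endpoints (protocol 8.3.1, SAP 3.2.1), and safety is the primary objective.

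**Limits.** SAP "Appendix Table 4. Vital Sign Abnormalities of Interest" has one column headed "Markedly Abnormal Criteria Lower limit" and one for the upper limit. Systolic and diastolic pressure, pulse, respiratory rate and temperature each get a single pair of absolute values. Weight is the exception, with a criterion of a 7% decrease or more.

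**Tables.** SAP 5.8.5 says: "Frequency tables of patients with potentially clinically significant vital sign values will be generated". It also plans the total number of such values, and summaries of baseline, highest/lowest and final observation with change from Baseline. Treatment-emergent status is mentioned only next to the listings.

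**Protocol.** Section 14.8.2.2 planned by-visit summaries and frequency tables of predefined-change abnormalities. SAP 6.1 declares that by-visit summaries of vital signs are dropped in favour of listings. Its visible text does not mention the missing change criterion and ends by stating that nothing else has changed.

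**Readings.** Treated boys receive "once weekly IV infusions of 30 mg/kg eteplirsen for up to 96 weeks" (protocol 8.1). Vital signs are taken "within approximately 30 minutes prior to infusion and approximately 5, 30, and 60 minutes after the end of the infusion" (protocol 11.3.2). For a boy without an infusion reaction after the first year, "vital signs may be reduced to pre-infusion and 30 minutes after the end of infusion".

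**The concern.** A count of patients with at least one value beyond a fixed limit rises with the number of values taken. With hundreds of readings per boy, one stray reading is enough to place him in the table. Nothing stated in 5.8.5 keeps out a boy who was already beyond the limit at Baseline. The companion count of total values has no reading denominator, so it grows in the same way.

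The readings are timed around each infusion, so they could show whether vital signs shift after dosing. The visible plan contains no same-day post- minus pre-infusion summary. Because the by-visit summaries are also gone, the abnormality table and the highest/lowest summary carry more of the safety description than the protocol intended, and the highest/lowest value is itself an extreme over many readings. At stake is how informative a listed safety endpoint will be.

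**Working it through.** The documents give no expected abnormality rate, so there is no planned figure to reproduce. The reading counts come from the schedule; the crossing rates and the correlation are assumptions.

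**1. Readings per treated boy, all 96 infusions given**
- Four readings throughout: 96 × 4 = 384.
- Reduced to two after Week 52 throughout: 52 × 4 + 44 × 2 = 208 + 88 = 296.
- The pre-dose reading on Day 1 would normally be Baseline (SAP 4.8), leaving 383 or 295; the results below do not change materially.
- Missed doses or early stopping lower these counts. Weight is scheduled about every 4 weeks, so they do not apply to it.
- Untreated boys have six scheduled post-baseline visits (Weeks 12, 24, 36, 48, 72, 96; protocol Section 3).

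**2. Chance of at least one flag per variable, independent readings:** 1 − (1 − p)^n

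| p per reading (assumed) | n = 296 | n = 384 | n = 6 |
|---|---|---|---|
| 0.1% | 26% | 32% | 0.6% |
| 0.5% | 77% | 85% | 3% |
| 1% | 95% | 98% | 6% |

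For example, 1 − 0.99^384 = 0.979. A 95% chance of a flag needs p = 1 − 0.05^(1/n), which is 0.78% for n = 384 and 1.01% for n = 296.

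**3. The same chance with readings correlated within a boy.** Beta-binomial with intraclass correlation ρ: 1 − B(a, b + n)/B(a, b), where a = p(1/ρ − 1) and b = (1 − p)(1/ρ − 1). With ρ = 0.1, 1/ρ − 1 = 9; at p = 1%, a = 0.09 and b = 8.91.

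| p per reading (assumed) | n = 296 | n = 384 | n = 6 |
|---|---|---|---|
| 0.5% | 15% | 16% | 2% |
| 1% | 28% | 29% | 5% |
| 2% | 48% | 50% | 9% |
| 5% | 80% | 82% | 22% |

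At p = 1% and n = 384, ρ = 0.05 gives 44% and ρ = 0.2 gives 17%.

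**4. What this shows.** The level of the patient count depends heavily on p and ρ, neither of which the documents supply. Its dependence on n does not go away: at ρ = 0.1 and equal p, 384 readings flag a boy about 6 times as often as six readings at p = 1% (0.292/0.047) and about 4 times as often at p = 5% (0.824/0.217). The percentage of readings flagged has expectation p whatever n is.

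**5. Text comparison.** Protocol 14.8.2.2 refers to predefined change. SAP Appendix Table 1 has predefined-change columns and multiples of baseline for several chemistry tests. Appendix Table 4 has a change criterion for weight only.

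**The case against.** **The size is not established.** Repeat readings in one boy are unlikely to be independent, and no crossing rate is given. This stands. A reader might infer that the table will flag almost everyone; the documents do not support that.

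**The any-reading rule is inferred.** For laboratory tests SAP 5.8.4 says a value at any time point counts. Section 5.8.5 does not say so for vital signs and refers to selected time points elsewhere. This stands as a caveat: the calculation is conditional on any reading counting. It also shows that the rule needs stating.

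**Age bands.** A reader might infer from "Appendix Table 5. Electrocardiogram and Echocardiogram Abnormalities of Interest" that Table 4 wrongly lacks them. The ECG bands split at 12 years, and boys enter at 4 to 6 and are followed for about two years, so only one band applies to this cohort. Whether the fixed limits suit the age range needs paediatric references that the documents do not contain.

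**Treated versus untreated.** The gap in reading counts might be read as biasing a comparison. SAP 6.1 rules out any direct comparison: only seven untreated boys enrolled and most left early. The groups are still tabulated by group, but no planned inference is affected.

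**Partly covered elsewhere.** SAP 5.8.5 reports total flagged values, the largest absolute change from Baseline for both pressures and respiratory rate, and listings marking treatment-emergent abnormalities. SAP 5.8.2 analyses infusion-related reactions separately. So the detection of infusion effects does not rest on this table alone. None of these items supplies a reading denominator or a paired pre/post summary.

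**Redaction and wording.** Text after the treatment-emergent laboratory heading in SAP 4.8, and some entries in 6.1, are blacked out; a vital-sign rule or a declared departure could sit there. The protocol phrase about predefined change is also garbled, though the word change is plain.

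**Conclusion.** The point holds in a limited form. Five of the six Table 4 rows are fixed limits without a change condition, contrary to protocol 14.8.2.2, and the visible SAP does not declare it. The counts in 5.8.5 have no stated treatment-emergent condition and no denominator of readings, and no post- minus pre-infusion summary is planned.

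If any reading counts, the patient-level table may flag many or most treated boys and so discriminate poorly. For 296 to 384 readings the illustrated range is 77% to 98% at 0.5% to 1% per reading under independence. At 1% with a within-boy correlation of 0.1 it is only 28% to 29%. All of these rest on assumed rates and on completed dosing. What rests on the schedule and the any-reading rule alone is that the count depends on how many readings are taken.

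**What to change.** In SAP 5.8.5 and Appendix Table 4:

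1. State which readings enter the frequency table, and count only treatment-emergent crossings, meaning those not present at Baseline. This removes boys already beyond a limit at the start but does not remove the effect of many readings.
2. Add a change-from-Baseline condition to the five fixed-limit rows, in line with protocol 14.8.2.2, or list the departure in SAP 6.1.
3. Report flagged readings as a percentage of readings taken, next to the patient count. This is the item that deals with the number of readings.
4. Summarise post-infusion minus same-day pre-infusion change for each vital sign.

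The cost is a little more programming and a somewhat longer table set. All the data are already collected under protocol 11.3.2. New age-specific limits are not part of this fix.

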Appendix Table 5. Electrocardiogram and Echocardiogram Abnormalities of Interest

Variable	Units	LLN	ULN	Age Group (years)	Markedly Abnormal Criteria
Heart rate	Beats per minute	60	130		NA
QTcF interval	msec	NA	NA	All	Screening Visit >450
				<12	>480
				≥12	>500
				All	<320 Increase >60 >450 >480 >500
QRS interval	msec	NA	NA	<12	IVCD or any QRS conduction disturbance with a QRS >110 msec
				≥12	IVCD or any QRS conduction disturbance with a QRS >120msec
PR interval	msec	NA	NA	<12	>190
				≥12	>220
Left ventricular ejection fraction	%	NA	NA	All	<55%
Fractional shortening	%	NA	NA	All	<29%

IVCD = intraventricular conduction delay; LLN = lower limit of normal; NA = not applicable; QTcF= QT interval Fridericia corrected; ULN = upper limit of normal
